7.2 Procedures for Discontinuation of a Patient from the Study

A patient who prematurely discontinues participation in the study will always be asked about the reason(s) for discontinuation and the presence of any AEs. If possible, they will be seen by the Investigator and assessed according to the procedures scheduled for the End of Study/Early Termination visit. Any ongoing AEs will be followed as described in Section 8.4.7.

7.3 Patient Replacement

Patient replacement is not planned.

7.4 Loss of Patients to Follow-Up

A patient will be considered lost to follow-up if he or she repeatedly fails to return for scheduled visits and is unable to be contacted by the clinic/investigational site until and including Visit 9/End of Study/Early Termination visit.

The following actions must be taken if a patient fails to return to the clinic for a required study visit or fails to be available for a telephone visit:

- The clinic/investigational site must attempt to contact the patient and reschedule the missed visit as soon as possible (and within the visit window, where one is defined) and counsel the patient on the importance of maintaining the assigned visit schedule and ascertain whether or not the patient wishes to and/or should continue in the study.
- In cases in which the patient missed one or more visits, the Investigator or Designee must make every effort to regain contact with the patient (where possible, three telephone calls and, if necessary, a certified letter to the patient's last known mailing address or local equivalent methods). The last attempt to contact the patient must be at the time for Visit 9. These contact attempts should be documented in the patient's medical record.

8 Study Assessments and Procedures

The study assessments are described in the sections below and the timing of these assessments are detailed in the SoA table (see Table 1).

The Principal Investigator will provide the Sponsor/Designee with all data produced during the study from the scheduled study assessments. He/she ensures the accuracy, completeness, legibility, and timeliness of the data reported to Sponsor/Designee in the electronic CRF (eCRF) and in all required reports.

It is important that PK blood sampling occurs as close as possible to scheduled time and is always accompanied with the time for the latest study medication tablet administration. In order to achieve this, the preferred timing priority order at a particular time point is:

- QOLRAD completion
- Blood samples for PK
- Safety laboratory samples
- ECG, vital signs, physical examination
- Investigator assessment
- Study drug administration

The actual sampling time and the time for the latest study medication tablet administration should always be recorded in the eCRF and will be used in the calculation of the PK parameters.

Blood samples will be drawn by venipuncture or an indwelling venous catheter at time-points specified in the detailed schedule of events in SoA (Table 1).

Detailed instructions for collection of samples will be provided in the laboratory manual.

The maximum volume of blood samples (safety samples and PK samples) collected during the study from each patient, including extra assessments that may be required, will not exceed 450 mL (i.e., less than the volume drawn during a regular blood donation).

8.1 Demographics and Other Baseline Characteristics

8.1.1 Informed Consent

Signed informed consent must be obtained before any screening procedures are initiated. The informed consent procedure is further described in Section 10.1.3.

8.1.2 Eligibility Criteria

Eligibility criteria should be checked during screening period and confirmed prior to inclusion/randomization. The criteria are specified in Sections 5.1 and 5.2.

8.1.3 Demographic Information

The following demographic data will be recorded: gender, age, and ethnic origin.

8.1.4 Weight and Height

Weight and height will be measured wearing light clothes and without shoes. Body mass index (BMI) will be calculated from the height and weight recorded and rounded off to the nearest whole number.

The body weight recorded at screening will be used for determination of eligibility and the body weight recorded at baseline, after the 4-week double-blind period and at the End of Study is a safety assessment. The method of weight assessment should be the same across all visits.

8.1.5 Medical/Surgical History

Medical/surgical history will be obtained by patient interview in order to verify that the eligibility criteria are met.

Medical history includes recent medical history, previous medical history (only significant medical or surgical illness), smoking, alcohol and intake of drugs of abuse and/or anabolic steroids.

8.1.6 Prior and Concomitant Medication

Prior medication will be obtained by patient interview in order to verify that the eligibility criteria are met (see also Section 5.3.2).

Medications are classified as prior if the stop date was before or on the day of the first dose administration (pre-dose) and as concomitant if ongoing on the day of the first dose administration, stopped after the first dose administration or started after the first dose administration.

Any use of concomitant medication from screening until the End of Study/Early Termination visit must be documented appropriately in the patient's eCRF. Relevant information (i.e., name of medication, total daily dose, unit, start and stop dates, reason for use if consistent with the definition of an AE) must be recorded. All changes in medication should be noted in the eCRF.

8.1.7 Serology (HIV and Hepatitis B/C Virus) Testing

Patients will be tested for HIV and hepatitis B surface antigen (HBsAg), antibody to hepatitis B core antigen (anti-HBcAg), antibody to hepatitis C virus (anti-HCV at central lab) prior to inclusion/randomization into the study in order to assess eligibility and protect personnel handling the blood samples.

8.1.8 Pregnancy Test

All women of childbearing potential will undergo a serum pregnancy test at screening and a urine pregnancy test (dipstick) prior to administration of study drug dose at Visit 5, and at End of Study/Early Termination.

8.1.9 Urine Drug Screen

Urine will be screened for drugs of abuse at screening using local drug screen tests (see the laboratory manual). Additional random tests can be performed during the study period.

8.2 Efficacy Assessments

Upper endoscopy for the examination of esophagus will be used to confirm patient eligibility as well as the confirmation of the primary endpoint. Imaging data must meet quality standards for adequate LA grading and must be accompanied by a report and videos/digital images to allow retrospective analysis of the endoscopy findings. The endoscopy has to be performed by an experienced endoscopist. The patient has to be fasting prior to endoscopy, i.e., drinking, eating, and smoking are not allowed from midnight prior to the assessment. The index/screening endoscopy must be taken within seven (7) days of the planned treatment day. Endoscopies taken prior to informed consent signatures can be used once the patient agrees to participate in the study and signs the informed consent. The endoscopy examinations must be recorded on a video

shot/digital images. The length, views and other technical specifications of the videos/digital images are described in the Image Acquisition Guidelines, separate document.

The endoscopy videos/digital images will be evaluated by Investigator or endoscopy specialist, as required. Grade of erosive esophagitis due to GERD will be determined by the appropriately trained Investigator or endoscopist according to the LA classification (see Appendix 8). The LA grading of the erosive esophagitis due to GERD should be documented in the endoscopy report.

The endoscopy videos/digital images will be collected into a central database, with the appropriate anonymization. All videos and digital images will be centrally reviewed retrospectively. This review will include reassessment of the LA grading and other findings which may constitute exclusion criterion. The central reading evaluation will override the investigators evaluations. Data obtained from patients deemed to have been ineligible for study enrollment following the retrospective analysis will be excluded from the per protocol analysis.

8.3 Safety Assessments

8.3.1 Physical Examinations

A complete physical examination will be performed as designated on the SoA and will include assessments of the head, eyes, ears, nose, throat, skin, thyroid, neurological, lungs, cardiovascular system, abdomen (including liver and spleen), lymph nodes, genitourinary system (optional) and extremities (musculoskeletal system).

8.3.2 Weight and BMI

Weight will be measured wearing light clothes and without shoes as designated on the SoA. The method of weight assessment will be the same across all visits. Body mass index (BMI) unit is kg/m^2 and calculated as weight in kg and height in meter.

8.3.3 Vital Signs

Examination of vital signs will be performed as designated on the SoA. Systolic and diastolic BP and heart rate (pulse) will be measured in supine position after 10 min of rest. Body temperature and respiratory rate will be measured pre-dose.

8.3.4 Resting 12-lead Electrocardiograms

Single 12-lead ECG will be recorded as designated on the SoA in supine position after 10 min of rest using an ECG machine. Heart rate and PQ/PR, QRS, QT and QTcF intervals will be recorded. Safety ECGs will be reviewed and interpreted on-site by the Investigator.

Abnormalities in an ECG will be assessed as “clinically significant” or “not clinically significant.” An ECG abnormality may meet the criteria of an AE as described in this protocol (see Section 8.4).

8.3.5 Clinical Safety Laboratory Assessments

Blood samples for analysis of clinical chemistry, hematology and coagulation parameters will be collected through venipuncture or an indwelling venous catheter and sent to the certified clinical chemistry laboratory and analyzed by routine analytical methods. Urine laboratory analysis will be performed at the research clinic/investigational site using dip sticks. Additionally, local testing at site includes urine drug abuse test and urine pregnancy test (dipstick) will be performed. For details, see the laboratory manual.

The following safety laboratory parameters will be assessed at time-points defined in SoA (Table 1):

Clinical Chemistry Alanine aminotransferase (ALAT) Alkaline phosphatase (ALP) Albumin Aspartate aminotransferase (ASAT) Bilirubin (total and conjugated) Calcium Chloride Creatinine Gamma-glutamyl transferase (GGT) Magnesium Phosphorous Potassium Sodium Urea nitrogen Uric acid Gastrin	Hematology Hematocrit Hemoglobin (Hb) Platelet count Red blood cell (RBC) count White blood cell (WBC) count with differential count
	Coagulation International Normalized Ratio
	Urinalysis (dip stick) Glucose Hemoglobin/erythrocytes Nitrite Protein Specific gravity pH Ketones
Viral serology Hepatitis B (HBsAg) Anti-hepatitis B core antigen (Anti-HBcAg)	Other Urine pregnancy test (HCG) ¹ Follicle stimulating hormone (FSH) ²

Hepatitis C antibody (anti-HCV)	Urine drug abuse screen ³
Human immunodeficiency virus (HIV-1 and -2)	H. pylori ⁴

¹ Women of childbearing potential only (local urine test at site)

² At screening, post-menopausal women only, as applicable (central laboratory)

³ At screening, local urine sample at site

⁴ *H. pylori* result will not be needed for randomization (central laboratory)

8.3.6 Concomitant Medication

Prior medication will be obtained by patient interview in order to verify that the eligibility criteria are met (see also Section 6.6).

Medications are classified as prior if the stop date was before or on the day of the first dose administration (pre-dose), and as concomitant if ongoing on the day of the first dose administration, stopped after the first dose administration or started after the first dose administration.

8.3.7 Reflux Related Symptoms Assessed Based on PRO

Reflux related symptoms will be assessed based on QOLRAD, which is a PRO developed by Wiklund et al in 1998 [8]. It has been translated and evaluated in multiple languages. The heartburn version of the QOLRAD is a disease specific instrument and contains 25 questions addressing concerns associated with gastrointestinal symptoms. The questions are rated on a seven-grade Likert scale; the lower the value, the more severe the impact on daily functions. The questions are categorized into five domains: emotional distress (six questions), sleep disturbance (five questions), vitality (three questions), food/drink problems (six questions) and physical/social functioning (five questions). It will be assessed at baseline, week 1, 2, and 4 (see Table 1). The QOLRAD will be completed pre-dose by patients at Visits 2, 3, 4, 5, and 9 (please refer to SoA).

Reflux related symptoms will be also assessed based on a modified RESQ-eDiary; an electronic symptom diary developed for use in partial responders to PPI. RESQ-eD has three Domains (i.e. Heartburn, Other GERD signs/symptoms and Regurgitations/Reflux) and eight Items. Patients will be asked to report every 12-hours, once before the morning dose and once before the evening dose of the IMP.

8.3.8 Reflux Related Symptoms Assessed by Investigator

Symptoms of GERD may include: heartburn (defined as a retrosternal burning pain rising from the epigastrium which may radiate into the pharynx), acid regurgitation (upward flow of sour

fluid toward the mouth), dysphagia, epigastric pain/discomfort, retrosternal tightness, burping/belching, nausea/vomiting, fullness, lower abdominal pain, flatulence, coughing.

At each visit, Investigator will assess the severity of patients' heartburn, regurgitation and dysphagia in the 7 days prior to the visit. The assessment will include both the severity grade and the frequency of symptoms. Assessments will be captured in EDC.

The potential frequency is defined as 7-graded Likert scale:

- All of the time;
- Most of the time;
- Quite a lot of the time;
- Some of the time;
- A little of the time;
- Hardly any of the time;
- None of the time.

Symptoms are scored as follows:

- none (no complaints),
- mild (aware of symptom, but easily tolerated),
- moderate (discomforting symptom, sufficient to cause interference with normal daily activities and/or sleep),
- severe (incapacitating symptom, with inability to perform normal daily activities and/or sleep).

8.3.9 Pharmacokinetic Samples and Analysis

Venous blood samples (approximately 5 mL, exact details are provided in the laboratory manual) for the determination of plasma concentrations of linaprazan and X842 after administration of the study drug, will be collected at the pre-specified time-points (see Table 1).

The date and time of collection of each sample and the time for the latest study drug administration will be recorded in the eCRF. PK samples will be collected 12 hours after the previous study drug dose administration or as close to this timepoint as possible, but always pre-dose (close before the first and the second dose administration at Days 7, 14 and 28).

Plasma samples for determination of plasma concentrations of linaprazan and X842 will be analyzed by means of a validated LC-MS/MS method (see the laboratory manual). The details of

the analytical method used will be described in a separate bioanalytical report. Detailed instructions for collection, handling, labeling, storage and shipment of samples will be provided in the laboratory manual.

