1. Including smoking (current status), alcohol consumption, and intake of drug of abuse.
2. Height only at screening
3. Human immunodeficiency virus (HIV), hepatitis B surface antigen (HBsAg), hepatitis B core antigen (anti-HBcAg), antibody to hepatitis C virus (anti-HCV) testing at central and/or local laboratory. Patient should discontinue the study if result from central laboratory is positive.
4. Systolic and diastolic blood pressure (BP) [mmHg], heart rate [beats per minute], body temperature and respiratory rate [per minute].
5. Hematology, blood chemistry, coagulation (central laboratory), urinalysis (at site). Serum gastrin at screening and at Visit 5 (central laboratory).
6. *H. pylori* will be analyzed in central laboratory from serum and the result will not be needed for randomization.
7. Women of childbearing potential only. Serum pregnancy test at central laboratory at screening and urine pregnancy test at clinic/investigational site prior to the dose administration at Visit 5, and at End of Study / Early Termination.
8. PK measured in all patients just before the first and the second dose on the day of the visit. At all PK sampling occasions, the time since latest study drug administration must be noted in the case report form (CRF). Pharmacokinetic samples will be collected 12 hours after the previous study drug dose administration or as close to this timepoint as possible, however, still pre-dose.
9. QOLRAD assessment must be done pre-dose. QOLRAD will be completed by patients during site visits at Visit 2, 3, 4, 5 and 9.
10. Patients will be trained on how to complete the symptoms diary during Visit 2 and the actual diary will be provided at Visit 2.

11. At each visit, Investigator should assess the severity of patients' heartburn, regurgitation and dysphagia in the 7 days prior to the visit. The assessment will include both the severity grade and the frequency of symptoms. Symptoms are scored as follows: none (no complaints), mild (aware of symptom, but easily tolerated), moderate (discomforting symptom, sufficient to cause interference with normal daily activities and/or sleep), severe (incapacitating symptom, with inability to perform normal daily activities and/or sleep)
12. Collection of AEs will start directly after the informed consent form (ICF) has been signed. During the screening period, only AEs related to study procedure will be reported.
13. For definitions of prior and concomitant medication, see Section 8.1.6.

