4.1 Overall Design

The study will be conducted in multiple centers in Europe and the US. This will be a randomized, double-blind, active comparator-controlled study with a parallel group design including four arms with X842 and one arm with lansoprazole. Pharmacokinetic (PK) blood sampling pre-dose, close before the first and the second dose administration will be performed at Day 7, Day 14 and Day 28 visits days in all patients. Approximately 240 patients with erosive esophagitis due to GERD LA grade C or D and patients with erosive esophagitis due to GERD LA grade A or B with at least partial symptom response but still endoscopically unhealed after 8 weeks history of standard treatment healing course with PPI, will be randomized in order to have 200 evaluable patients.

Randomization to one of the treatments with X842 BID 25 mg, 50 mg, 75 mg, 100 mg, or lansoprazole 30 mg once daily (QD) will be based on a 1:1:1:1:1 scheme. One site cannot enroll more than 20% of the overall number of patients (48 patients per site).

The duration of each patient's participation in the study, including screening, blind treatment period and open-label treatment period, will be approximately 60 days. The patients will be randomized for 4 weeks (28 days, -2/+5 days) of double-blind treatment and will be provided with IMP for 35 days (including one additional blister pack dispensed at Visit 2/Day 0) to allow for treatment up to the visit window. All patients will have an endoscopic evaluation after 4 weeks treatment. Following the endoscopic evaluation, all patients will receive subsequent 4 weeks of open-label treatment with lansoprazole 30 mg QD. Repeated symptom evaluation to detect symptom pattern will be assessed during this period. The study design is shown below (Figure 2).

Figure 2 **Study Design**

The study will comprise 6 visits at the site and 3 telephone visits. Based on the endoscopy findings and/or signed informed consent form (ICF), the screening visit (Visit 1) will take place not more than 7 working days prior to randomization and the first dose administration (Visit 2). All patients will then visit the study clinic/investigational site after 7 (Visit 3), 14 (Visit 4) and 28 days (Visit 5) and at the End of Study/Early Termination visit (Visit 9). There are 3 weekly telephone visits after Visit 5. See Table 1.

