6.2 Preparation/Handling/Storage/Accountability

The blister packs containing the study medication will be dispensed as per randomization schedule by a site pharmacist or a registered nurse under supervision of other site personnel.

The Investigator will maintain a Drug Dispensing Log detailing the dates and quantities of study medication received, dispensed to and used by each patient and study medication returned or destroyed at the end of the study. Any discrepancies between dispensed and returned study drug must be explained and documented. Products deliberately and/or accidentally destroyed by the Investigator/pharmacy or the patient, must be accounted for. Patients will receive one additional blister pack at Visit 2/Day 0 to keep overage in case they return within the allowed visit window. Patients should return this additional blister pack for accountability at every visit and returned on Visit 5.

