9.4.9 Other Analyses

Descriptive statistics for the C-trough will be presented by treatment group with number of measurements, arithmetic mean, SD, CV, median, minimum, maximum, geometric mean, geometric CV%.

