4.10.4 Exploratory efficacy endpoint

CCI

CCI

[figure not shown]
Pre-dose plasma concentrations will be collected twice daily, pre-dose, before the first and the second dose administration at Day 7, Day 14 and Day 28 visits in all patients.

The following descriptive statistics will be presented for plasma concentrations obtained at each nominal time point: n, arithmetic mean, SD, coefficient of variation (CV%), geometric mean, geometric CV%, median, minimum and maximum values.

CCI

CCI

CCI

CCI

CCI

CCI

Parexel International

Cinclus Pharma AG

Protocol #CX842A2201

Statistical Analysis Plan

CC1

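### The protocol asks for a Day 28 PK sample before a second X842 dose that it does not clearly provide, so the time since the last dose is undefined, and the readable analysis text has no rule for it

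*Protocol*

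**What the plan says.** **Sampling.** Protocol 8.3.9 sets the target time: "PK samples will be collected 12 hours after the previous study drug dose administration or as close to this timepoint as possible, but always pre-dose". It names the occasions as "close before the first and the second dose administration at Days 7, 14 and 28". Footnote 8 to the Schedule of Assessments (Protocol 1.3) puts both samples on the visit day: "PK measured in all patients just before the first and the second dose on the day of the visit". Protocol 4.1 and SAP 3.1 repeat the schedule and treat Day 28 like Days 7 and 14.

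**Treatment on Day 28.** Protocol 4.2 treats the Week 4 endoscopy as the point where blinded treatment stops. Protocol 4.1 continues: "Following the endoscopic evaluation, all patients will receive subsequent 4 weeks of open-label treatment with lansoprazole 30 mg QD". Under Protocol 6.1 that open-label regimen is a single capsule each morning. The Schedule of Assessments dispenses blinded drug at Visits 2, 3 and 4 only, and open-label lansoprazole at Visit 5. On the spare blinded supply, Protocol 6.2 says: "Patients should return this additional blister pack for accountability at every visit and returned on Visit 5".

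**The fast.** Before each endoscopy, "drinking, eating, and smoking are not allowed from midnight prior to the assessment" (Protocol 8.2). The synopsis has study drug taken with 100 mL of water.

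**Analysis.** Protocol 9.4.9: "Descriptive statistics for the C-trough will be presented by treatment group", with no time window. SAP 4.10.4: "The following descriptive statistics will be presented for plasma concentrations obtained at each nominal time point". Much of the rest of SAP 4.10.4 is redacted. Protocol 8 has the actual sampling time and the time of the latest tablet recorded, for use in calculating PK parameters.

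**The concern.** A pre-dose sample 12 hours after the previous dose is well defined under twice-daily dosing. On Day 28 the twice-daily regimen ends and a once-daily morning regimen follows, so there is no clear second X842 dose for the second sample to precede. The morning dose is also uncertain, because the patient is fasting for endoscopy and no passage says whether a blinded dose is taken before it, after it or not at all. Sites could all follow the text and still draw this sample at quite different times after the last X842 tablet.

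The sample concerned is the evening pre-dose value. Protocol 2.1.1.6 reports that in Phase 1 this value had low variability and tracked pH control closely, and Protocol 2.2 names the PK profile as one of three inputs to the Phase 3 dose choice. Protocol 2.1 and 2.1.1.6 already describe lower linaprazan levels on repeated dosing. A Day 28 fall caused only by sampling time could be read as more of the same, and a sample drawn early could hide a real fall.

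**Working it through.** **1. The plan's own figure.** Twice-daily dosing gives an interval of 24/2 = 12 h. This matches the stated target for both samples on Days 7 and 14 and for the morning sample on Day 28, that is, for five of the six samples per patient.

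**2. Where a 28-day course ends.** Protocol 6.4 starts dosing on Day 0, either up to 2 pm or at 8 pm. Assume dose times of 08:00 and 20:00. Twenty-eight days give 2 × 28 = 56 doses, and the last falls 12 × 55 = 660 h after the first.
- Start at 08:00 on Day 0: 8 + 660 = 668 = 27 × 24 + 20, so Day 27 at 20:00.
- Start at 20:00 on Day 0: 20 + 660 = 680 = 28 × 24 + 8, so Day 28 at 08:00.

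Neither course reaches an evening dose on Day 28. The count is only indicative, because the visit may move by −2/+5 days. Supply is not the obstacle: 35 days dispensed against a maximum of 28 + 5 = 33 leaves 2 spare. What prevents a second dose is the switch of treatment at Visit 5.

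**3. Time since the last X842 dose at the second Day 28 sample.**

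| Second sample drawn | Morning X842 taken at 08:00 | Last X842 on Day 27 at 20:00 |
|---|---|---|
| 10:00 to 18:00 | 2 to 10 h | 14 to 22 h |
| 20:00 | 12 h | 24 h |

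If the instruction is read strictly, as a sample that must precede a second dose, it may not be obtainable at all.

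**4. What the timing could do to the value.** The readable text gives no half-life. Assume mono-exponential decline over a range of half-lives t:
- 24 h against 12 h: ratio = 0.5^(12/t).
- 9 h against 12 h (9 h is an illustrative early draw): ratio = 2^(3/t).

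| Assumed half-life | 24 h / 12 h | Change | 9 h / 12 h | Change |
|---|---|---|---|---|
| 4 h | 0.125 | −88% | 1.68 | +68% |
| 6 h | 0.25 | −75% | 1.41 | +41% |
| 10 h | 0.435 | −56% | 1.23 | +23% |

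Widening the range to 3 and 12 h gives 24 h / 12 h ratios of 0.06 and 0.50. For scale, the step from 75 to 100 mg is 100/75 − 1 = 33%. Protocol 4.3 agrees in direction, at a different dose and regimen: after 150 mg once daily, concentrations indicated pH control up to 12 h but not at 22 and 24 h.

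**5. Reach.** Three days with two samples each give six per patient. One of the six, or one of the three second-dose samples, is open to this. The X842 arms hold 4 × 48 = 192 planned patients, which is an upper bound.

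**The case against.** A trough depends on the time since the previous dose, not on whether another dose follows. The documents do expect a dose at Visit 5: Protocol 8.1.8 places the pregnancy test before it, Protocol 8.3.7 has QOLRAD completed pre-dose at that visit, and the visit order in Protocol 8 ends with study drug administration. If that dose is blinded X842 and blood is drawn 12 hours later, the value is a true trough. Protocol 6.2 speaks only of the additional pack, and no passage gives the day of the first open-label capsule. All of this stands. It rules out saying that no X842 is taken on Day 28, but the documents do not say whether the Visit 5 dose is blinded or open-label.

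Protocol 8.3.9 ties the sample to the dose, so a late morning dose should move the sample later. That is fair, but the clause allowing the nearest feasible time also permits an early draw.

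Actual times are recorded and used for PK parameters, and the redacted part of SAP 4.10.4 may contain a handling rule. The second possibility cannot be excluded. The first does not settle the matter: C-trough, the only PK quantity in the readable analysis text, is an observed concentration, so its timing matters only if a rule decides which samples qualify.

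The summary is exploratory and descriptive. Under SAP 4.10.4 the Day 28 second sample would have its own row, leaving Days 7 and 14 intact. A timing shift common to all X842 arms would leave the ratios between doses unchanged under the same mono-exponential assumption. These points stand and limit the consequence. They do not cover a row in which patients were sampled at different intervals.

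**Conclusion.** The inconsistency is in readable text and holds. The plan requires a Day 28 sample before a second dose, does not clearly provide that dose as X842, and does not say whether a blinded morning dose is taken around the endoscopy. The interval since the last X842 dose may be about 12 h, shorter, or up to about 24 h, or there may be no sample. The readable analysis text would place all of these in one nominal row, with no admission rule for C-trough.

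A reader might infer that the Day 28 evening value is in fact a 24-hour level reported as a 12-hour trough. The documents do not support that: a compliant 12-hour sample is possible, the timing of the last blinded and first open-label doses is not stated, and handling rules may sit in redacted text. Nor do they support a claim that dose selection would go wrong, since the primary dose-response model uses healing alone and the Day 7 and Day 14 evening samples are unaffected.

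Reach is at most one of six samples per X842 patient, in an exploratory descriptive summary. The percentage shifts rest on assumed half-lives and mono-exponential decline. The point still deserves correction, because the PK profile is a stated input to the Phase 3 dose choice and the remedy needs no new data.

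**What to change.** **Protocol.** Reconcile Sections 4.1, 4.2, 6.1, 6.2, 8.1.8, 8.2 and 8.3.9, with footnote 8 of the Schedule of Assessments, so that they agree on which study drug is taken on the Visit 5 day, when it is taken relative to the endoscopy, and what the second PK sample is timed against. Which arrangement is right is for the sponsor to decide.

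**SAP.** In 4.10.4, classify each PK sample by the recorded actual time since the last X842 tablet. Admit a sample to C-trough only within a window around 12 h fixed in advance, and report off-window Day 28 samples separately with their actual times. If the redacted text already does this, a cross-reference from the nominal-time summary is enough.

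**Cost.** One protocol clarification and one derivation rule, using times already collected. The downside is that some Day 28 second-sample values leave the C-trough table, so that row may rest on fewer patients than the others.
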